SNSF Swiss National Science Foundation

STH Soil-transmitted helminths

SUSAR Suspected unexpected serious adverse reaction

Swiss TPH Swiss Tropical and Public Health Institute

VAS Visual analogue scale

WHO World Health Organization

IV. Synopsis

Sponsor/Sponsor-	[name]. [name]
Investigator	
Study title	Efficacy, safety and acceptability of ascending doses of ivermectin in combination with albendazole for Trichuris trichiura infections in preschool-aged children: a single-blind randomised controlled doseranging trial
Short title	Ivermectin-albendazole combination for Trichuris trichiura —infected children
Study acronym	Iverped
Protocol version and date	v1, 08 May 2024
Trial registration	Registered on https://www.clinicaltrials.gov/ (NCT06184399)
Clinical phase	Phase 2 trial
Sample size	210 participants
Indication	Trichuris trichiura infection (eggs in stool)
Investigational and reference treatment	Ivermectin orodispersible mini-tablets (ODTs) co-administered with albendazole Reference: albendazole; ivermectin standard tablets co-administered with albendazole
Study rationale	To provide evidence on the optimal dose of co-administered ivermectin and albendazole in terms of efficacy, safety and acceptability in preschool-aged children (PSAC; aged 2-5 years) infected with T. trichiura . Additionally, to compare the pharmacokinetics of the newly developed ODTs and the standard ivermectin tablets in this age group.

Study objectives	Our primary objective is to determine the ivermectin dose-response							
	relationship in terms of cure rate (CR) in PSAC (2-5 years) infected with							
	T. trichiura, assessed at 14-21 days post-treatment by quadruplicat							
	Kato-Katz microscopy.							
	The secondary objectives of the trial are:							
	a) to determine the T. trichiura egg reduction rates (ERRs							
	treatments;							
	b) to determine the CRs and ERRs of treatments against Ascaris							
	lumbricoides and hookworm co-infection;							
	c) to evaluate the safety and tolerability of the treatments;							
	d) to characterize population pharmacokinetics (PK) of ivermectin							
	ODTs compared to standard tablets in T. trichiura infector							
	individuals;							
	e) to assess the acceptability of the treatments.							
	The exploratory objective of this trial is to assess the diagnostic							
	performance of FECPAKG2.							
Study design	Parallel randomised controlled dose-ranging trial							
Study product / intervention	Administration of a single oral dose of ivermectin ODT (100-400 $\mu g/kg$) and albendazole (400 mg)							
Comparator(s)	Albendazole (400 mg); ivermectin standard tablets (200 μ g/kg) and albendazole (400 mg)							
Key inclusion / Exclusion	Inclusion:							
criteria	• Individuals aged 2-5 years (24-71 months; confirmed by birth certificate or similar document);							
	 having given written informed consent signed by parents/caregivers; 							
	being able and willing to provide two stool samples at baseline and at fallow up assessment (14.21 days).							
	and at follow-up assessment (14-21 days);							
	having at least two out of four Kato-Katz slides positive for T trickium at baseline:							
	T. trichiura at baseline;							
	being able and willing to be examined by a study physician before and efter treatment.							
	before and after treatment.							
	Exclusion:							

Primary endpoints Secondary endpoints	 presence or signs of major systemic illness, e.g. fever (temporal body temperature of >38.0°C), severe anaemia (haemoglobin level of <70 g/l); history of severe acute disease or unmanaged, severe chronic disease (i.e., condition is not as therapeutically controlled as necessary); use of anthelminthic drugs during study period; known allergy to study medication (i.e., ivermectin or albendazole); being prescribed or taking concomitantly medication with known contraindications or drug interactions with the study medication; concurrent participation in other clinical trials. T. trichiura infection status of participants at 14-21 days post-treatment assessed by quadruplicate Kato-Katz A. lumbricoides and hookworm infection status and intensity of co-infected participants at 14-21 days post-treatment assessed by quadruplicate Kato-Katz Adverse events (AEs)
	 Population PK parameters of ivermectin ODTs and standard tablets in T. trichiura infected PSAC Acceptability (including palatability)
Exploratory endpoints	Diagnostic characteristics of FECPAKG2 (infection intensity, sensitivity, and specificity) compared to Kato-Katz
Interim analyses	None
Study duration	3 months
Schedule	05/2024: of first participant in (planned) 07/2024: of last participant out (planned)
Study centres	T. trichiura endemic villages, Wete district, Pemba Island, Tanzania

Measurements & procedures

For the initial diagnosis and efficacy assessment at 14-21 days posttreatment, two stool samples will be collected from each participant on two consecutive days. All stool samples will be examined for presence of T. trichiura, A. lumbricoides, and hookworm eggs with duplicate Kato-Katz thick smears assessed via bright-field microscopy. The medical history of the participants will be assessed with a standardised questionnaire, in addition to a clinical examination carried out by the study physician before treatment. Parents/caregivers will be interviewed before treatment and at three and 24 hours and 14-21 days post-treatment for the occurrence of AEs. Any potential AEs happening between 3 hours and the respective follow-up time points will be monitored by local healthcare workers and medical intervention provided if necessary. Each participant will be asked to provide a finger-prick blood sample for haemoglobin measurement at baseline. At the same time, anthropometric measurements (i.e. height, and weight) will be taken for all participants.

To determine PK parameters of ivermectin ODTs and standard tablets, a subsample of 12 study participants per relevant treatment arm (ivermectin ODT 200 μ g/kg and ivermectin tablet 200 μ g/kg) will be asked to provide a maximum of 5 micro blood samples per participant using finger pricks at defined time points between 1 hour and 24 hours. To determine the acceptability of ivermectin ODTs compared to standard tablets, the palatability of each formulation will be rated by children aged 4-5 years using a 100 mm visual analogue scale (VAS). Additionally, participants will complete a short questionnaire right after treatment administration.

Statistical analyses

An available case analysis (full analysis set according to the intention to treat principles) will be performed, including all participants with primary endpoint data. Additionally, a per-protocol analysis will be conducted. CRs will be calculated as the percentage of egg-positive participants at baseline who become egg-negative after treatment.

Geometric and arithmetic mean egg counts will be calculated for the different treatment arms before and after treatment to assess the corresponding ERRs. Bootstrap resampling with 5,000 replicates will be used to calculate 95% confidence intervals (CIs) for ERRs.

	Using the DoseFinding package of the statistical software environment
	R , E_{max} models will be implemented to predict the dose-response curves

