Trichuriasis is a parasitic disease caused by nematodes belonging to the group of soil-transmitted helminths (STH). It is estimated that around 400 million people harbour infections with *Trichuris trichiura* globally [1]. As it is the case for all STH infections, trichuriasis is mainly endemic in developing countries in tropical and subtropical regions, with highest burden among rural communities due to its link to poor sanitation [2].

Infection with *T. trichiura* occurs when ingesting embryonated eggs via soil-contaminated hands, drinking water or food. Having reached the small intestine, the eggs hatch realising the larvae. The larvae migrate directly into the cecum where they develop into adult worms and begin to oviposit. Eggs are excreted into the soil via the faeces, thereby closing the life cycle [3].

Acute symptoms of trichuriasis are generally mild or not apparent in infected individuals living in endemic areas [2, 4]. The main disease burden results from chronic infection and repeated re-infection, in which symptoms related to the location of adult worms such as abdominal pain may develop. Long-term infection compromises the life of people by hampering their physical and mental development, limiting their work performance and overall quality of life [4].

The recent World Health Organization (WHO) road map for neglected tropical diseases targets STH infections for near to global elimination as a public health problem by 2030 [5]. One important intervention to achieve this is preventive chemotherapy (PC) [5-7]. The aim of PC is to reduce worm burden and hence morbidity in endemic populations by regular large-scale administration of anthelminthic drugs to high-risk groups, *e.g.* preschool-aged and school-aged children [8, 9]. The frequency of such mass drug administration (MDA) depends on the local infection prevalence [8, 9]. At present, the benzimidazoles albendazole and mebendazole are the most widely used drugs for PC campaigns against STH infections [7, 10]. These drugs are characterized by high cure rates (CRs) against infections with *Ascaris lumbricoides* (>95%) and moderate CRs against hookworm infections (80%). However, at single oral doses suitable for MDA, these drugs have demonstrated unsatisfactory efficacy against *T. trichiura* infections [11, 12].

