The **secondary objectives** of the trial are:

- a) to determine the *T. trichiura* egg reduction rates (ERRs) of treatments;
- b) to determine the CRs and ERRs of treatments against *Ascaris lumbricoides* and hookworm co-infection;
- c) to evaluate the safety and tolerability of the treatments.
- d) to characterize population PK of ivermectin ODTs compared to standard tablets in *T. trichiura* infected individuals;
- e) to assess the acceptability of the treatments.

The **exploratory objective** of this trial is to assess the diagnostic performance of FECPAKG2.

4. Methodology

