4.1 Primary and secondary endpoint

Primary endpoint: *T. trichiura* infection status of participants at 14-21 days post-treatment assessed by quadruplicate Kato-Katz.

Secondary endpoints:

- *T. trichiura* infection intensity of participants at 14-21 days post-treatment assessed by quadruplicate Kato-Katz;
- *A. lumbricoides* and hookworm infection status and intensity of co-infected participants at 14-21 days post-treatment assessed by quadruplicate Kato-Katz;
- Tolerability of treatments (adverse events (AEs) at three and 24 hours and 14-21 days post-treatment;
- Population PK parameters of ivermectin ODTs and standard tablets in *T. trichiura* infected PSAC;
- Acceptability (including palatability).

Exploratory endpoints: Diagnostic characteristics of FECPAKG2 (infection intensity, sensitivity, and specificity) compared to Kato-Katz.

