4.3.4 Treatment of participants

All eligible participants will be treated with the respective treatment regimen according to their treatment arm assigned by randomisation at day 0. Ivermectin tablets (ODT and standard tablets) will be obtained from Liconsa, and an individual number of tablets according to bodyweight and dose will be administered. Albendazole will be the product of GSK (Zentel®) and a single tablet of 400 mg will be administered. Placebo tablets will be purchased from Zentiva Pharma GmbH, Germany.

The tablets will be handed out from four drug containers (placebo, ivermectin ODT, ivermectin standard tablets, and albendazole). According to the randomisation list, each person will receive either:

- (i) Placebo (number corresponding to 200 µg per kg bodyweight) plus a single tablet of albendazole
- (ii) 100 μg ivermectin ODT per kg bodyweight plus a single tablet of albendazole
- (iii) 200 µg ivermectin ODT per kg bodyweight plus a single tablet of albendazole

- (iv) 300 µg ivermectin ODT per kg bodyweight plus a single tablet of albendazole
- (v) 400 µg ivermectin ODT per kg bodyweight plus a single tablet of albendazole
- (vi) 200 µg ivermectin standard tablets per kg bodyweight plus a single tablet of albendazole

All drugs will be administered in the presence of the Principal Investigator (PI) and/or Co-PI, and ingestion confirmed. This will be recorded with the time and date of dosing. Participants will be asked to limit the use of any drugs other than those prescribed by the study medical team for the duration of the study as described in section 5.5. After ingestion of the medication, the participants will be observed for three hours to ensure retention of the drug. Vomiting within one hour post-dosing will require redosing. The participants will not be allowed more than one repeated dose. No re-administration will be needed for participants vomiting after one hour. The PI or the Co-PIs are responsible for drug accountability at the study site. Maintaining drug accountability includes careful and systematic study drug storage, handling, dispensing, and documentation of administration. Prior to administration, drugs will be stored at room temperature and protected from light and exposure to moisture in a secure area with limited access at the study site.

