8.3 Description of statistical methods

The primary analysis will use the full analysis set (available case population) according to the intention-to-treat principles defined as all randomised participants who provide any follow-up data. Only randomised participants not providing follow-up data as well as participants who were negative at baseline and erroneously randomised will be excluded from the analysis. In addition, a per-protocol analysis will be conducted. Eligibility for analysis sets will be determined before unblinding. CRs will be calculated as the percentage of egg-positive participants at baseline who become egg-negative after treatment.

EPG will be assessed by adding up the egg counts from the quadruplicate Kato-Katz thick smears and multiplying this number by a factor of six. Geometric and arithmetic mean egg counts will be calculated for the different treatment arms before and after treatment to assess the corresponding ERRs (see formula).

$$ERR = 1 - \frac{\frac{1}{n} e^{\sum \log(EPG_{follow-up} + 1)} - 1}{\frac{1}{n} e^{\sum \log(EPG_{baseline} + 1)} - 1}$$

Bootstrap resampling method with 5,000 replicates will be used to calculate 95% confidence intervals (CIs) for ERR point estimates. Using the DoseFinding package of the statistical software environment R, hyperbolic E_{max} models will be implemented to predict the curves of the dose-response in terms of CRs and ERRs.

Previous similar trials have shown that the proportion of participants lost to follow-up is usually far below 10%, therefore, no imputation of missing data will be performed. Infection status and egg counts of participants with incomplete data at follow-up (*i.e.* only one stool sample available at follow-up) will be estimated based on the available data. This means a participant is considered infected if any sample is positive and EPGs will be calculated as mean egg count of the available sample multiplied by 12.

The safety analysis set will include all treated participants. AEs will be evaluated descriptively focusing on the proportion of participants reporting symptoms before and after treatment in each arm.

Previously established nonlinear mixed-effects (NLME) models will be used to compare and determine PK parameters [21]. Concentrations are measured with a validated LC-MS/MS method [32]. Using NLME, the following key PK parameters will be calculated:

- C_{max} maximal plasma concentration
- t_{max} time to reach C_{max}

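### The only interval planned for an egg reduction rate has zero width (100% to 100%) in any arm where every co-infected child is egg-free at follow-up, and the plan has no rule for that case

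*Combined protocol and SAP*

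**What the plan says.** - Section 3, secondary objective (b): "to determine the CRs and ERRs of treatments against *Ascaris lumbricoides* and hookworm co-infection". Section 4.1 limits these endpoints to the co-infected participants.
- Section 8.3: "Bootstrap resampling method with 5,000 replicates will be used to calculate 95% confidence intervals (CIs) for ERR point estimates". The synopsis (Statistical analyses) says the same: "Bootstrap resampling with 5,000 replicates will be used to calculate 95% confidence intervals (CIs) for ERRs". Neither place limits the method to *T. trichiura*, names the type of bootstrap, or says what to do when an arm has no eggs at follow-up.
- Section 4.3.8 counts a child as cured when the follow-up stools show no eggs, so a cured child has a follow-up EPG of 0.
- Section 4.3.4 gives albendazole in all six arms: "a single tablet of 400 mg will be administered".
- Section 2 describes benzimidazoles by "high cure rates (CRs) against infections with *Ascaris lumbricoides* (>95" percent) and "moderate CRs against hookworm infections (80" percent).
- Section 5.2 makes entry depend on *T. trichiura* alone. The documents give no expected number of co-infected children, no minimum number for analysis, and no interval method for the cure rates of the co-infections.

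**The concern.** A nonparametric bootstrap can only reproduce variation that is in the sample. When every follow-up count is zero there is none, so the method reports complete certainty however few children stand behind it. For *A. lumbricoides* the protocol's own background figure makes all-zero arms an ordinary outcome.

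A results table built to the stated rule could then show 100% (100% to 100%) for an arm with a handful of co-infected children. It could sit beside an arm with one residual positive and an interval of real width. In a dose-ranging trial, such a pair invites a dose contrast that the data cannot support. No interval for the cure rate is planned that would show the reader how little information there is.

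**Working it through.** **Reference point: the plan's own figure.** Section 8.2 states a precision of about 10 percentage points for the *T. trichiura* dose-response curve, with 35 per arm and 10% loss. Fitting a hyperbolic Emax curve to the stated cure-rate sets with 31 to 32 evaluable per arm (35 × 0.9 = 31.5) gives a median 95% half-width of 10.5 to 10.7 points for the optimistic set and 9.9 to 10.1 for the pessimistic set. The figure reproduces, and nothing below affects it. The plan gives no precision figure for co-infection ERRs.

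**Step 1: the collapse.** ERR = 1 − (mean follow-up EPG) / (mean baseline EPG). If all *n* follow-up values are 0, the arithmetic follow-up mean is 0 in every resample. The geometric mean is exp[(1/n) Σ log(0 + 1)] − 1 = 0 as well. Every replicate gives ERR = 1 − 0 = 100%. A run with 5,000 replicates at n = 2, 3, 5, 10, 20 and 32 gave 100% to 100% each time for both means. Percentile, basic and normal bootstrap intervals all have zero width here, and BCa is undefined. The formula printed in section 8.3 has 1/n outside the exponent. Read literally it gives 100% or negligibly more, so the conclusion stands.

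**Step 2: how often in one arm.** P(all *n* egg-free) = CR^n, with CR = 0.95 as the edge of the background figure. The number co-infected is not in the documents, so *n* is an assumption. It is shown from 5 up to 32, which is about every evaluable child in an arm. For six arms of equal *n*, treated as independent, the number of collapsed arms is binomial.

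| n per arm | P(collapse) = 0.95^n | Expected arms of 6 | P(at least 2 arms) | P(at least 3 arms) |
|---|---|---|---|---|
| 5 | 77% | 4.6 | 99.7% | 97% |
| 10 | 60% | 3.6 | 96% | 82% |
| 20 | 36% | 2.2 | 70% | 37% |
| 32 | 19% | 1.2 | 33% | 9% |

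At a cure rate of 98%, P(at least 3 arms) is 99% at n = 10, 90% at n = 20 and 70% at n = 32. For hookworm at 80%, the chance per arm is 33% at n = 5, 11% at n = 10 and 1% at n = 20.

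**Step 3: what the data support in that case.** The exact (Clopper-Pearson) 95% lower limit for the cure rate with *n* of *n* cured is 0.025^(1/n): 48% (n = 5), 69% (n = 10), 83% (n = 20), 89% (n = 32). With 10 of 10 cured, up to 31% uncured remains compatible with the data. The bootstrap ERR interval is 100% to 100% at all four sizes.

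**Step 4: arms with at least one positive child.** This needs assumed egg counts:

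- *A. lumbricoides*: lognormal baseline, geometric mean 3000 EPG, log-SD 1.3; residual-to-baseline ratio with median 0.2 and log-SD 1.0; 95% cured.
- Hookworm: geometric mean 150 EPG, log-SD 1.2, median ratio 0.3 (log-SD taken as 1.0); 80% cured.

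Across simulation runs, coverage of the nominal 95% interval in such arms was:

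| Setting | Arithmetic ERR | Geometric ERR |
|---|---|---|
| *A. lumbricoides*, n = 10 | 79% to 84% | 96% or more |
| *A. lumbricoides*, n = 20 | 67% to 69% | 96% or more |
| Hookworm, n = 10 | 70% to 71% | 96% or more |

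**The case against.** The arithmetic of the collapse is not open to dispute. Its reach is, in four respects.

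- **Number of arms.** A reader might infer that several arms will certainly be affected. The documents do not support that, because no co-infection count is given. At 95% cure, at least three arms collapse with probability 82% at n = 10 but only 9% at n = 32. The 95% is also a background figure for benzimidazoles in general, not for this age group or site. It is quoted as a floor, though, and a higher cure rate raises every probability. This limits the claim but does not remove it.
- **Intervals with one or two positive children.** A reader might infer that these are also far too narrow for every ERR. That holds only for the arithmetic ERR and only under assumed distributions. The geometric ERR, the one whose formula section 8.3 prints, covers adequately once any child is positive.
- **Size of the error in the ERR.** Under the Step 4 populations the true *A. lumbricoides* ERR is about 99.99% (geometric) or 98.3% (arithmetic). An estimate of 100% is therefore off by about 0.01 or 1.7 points. One child in 10 left at 600 EPG moves the geometric ERR only to 99.97%. This stands: the fault lies in the stated certainty more than in the point estimate. It rests on egg counts that the trial has not yet observed.
- **Consequence.** This is one of several secondary objectives. No test, decision rule or sample size depends on it, and cure rates will be reported alongside. That stands too, although the cure rates have no planned interval.

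**Conclusion.** The concern holds within limits. The stated rule yields a zero-width 95% interval in every arm where all co-infected children are egg-free. This follows from the method and needs no assumption. It is a wrong error bar produced by the plan as written, which is more than an omitted detail.

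At 95% cure of *A. lumbricoides* the chance per arm is 77%, 60%, 36% and 19% for 5, 10, 20 and 32 co-infected children. How many arms are affected depends on a count that the documents do not give. The secondary weakness, under-coverage when some children stay positive, is marked for the arithmetic ERR only and depends on assumed egg counts. The primary analysis and the sample size are not affected.

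**What to change.** In section 8.3 and the synopsis, state two rules for the co-infections:

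1. For each arm and species, report the number co-infected and the number egg-free at follow-up, with an exact (Clopper-Pearson) 95% interval for the cure rate. For example, 10/10 gives a lower limit of 69% and 20/20 gives 83%.
2. When no eggs are found at follow-up in an arm, report the ERR as 100% and mark its interval as not estimable, in place of a bootstrap interval.

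A pooled six-arm *A. lumbricoides* result may be added as a descriptive supplement. It should not replace the per-arm results, because it averages over different ivermectin doses and objective (b) concerns the treatments.

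Two tempting alternatives should not be used:

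- **An ERR lower limit of 1 minus the exact upper limit for the proportion uncured.** With a baseline log-SD of 1.3, the heaviest 31% of children carry about 79% of the eggs. So 0 of 10 positive would allow an arithmetic ERR near 21%, not at least 69%. The same 31% left unchanged from a geometric mean of 3000 EPG still gives a geometric ERR of about 99.6%. The limit fits neither measure.
- **Dropping the bootstrap whenever fewer than five children are positive.** At 80% hookworm cure this would remove it in 97% of arms at n = 10 and 63% at n = 20, including geometric intervals that cover well.

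The cost is two or three sentences and a few lines of code, with no change to treatment, visits or sample size. The downside is that the co-infection results will look less certain.
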